**THE EFFECT OF REPOSITIONING FREQUENCY DETERMINED ACCORDING
TO BODY MASS INDEX ON PRESSURE ULCER DEVELOPMENT TIME:
RANDOMIZED CONTROLLED TRIAL**

ClinicalTrials.gov ID: [NCT05504980](https://clinicaltrials.gov/ct2/show/NCT05504980)

Document Date: June 30, 2023

Setting/Participants

This study was conducted in the intensive care and palliative care units of a university hospital between 01.07.2022 - 29.01.2023. The sampling volume that should be included in the sample of the study was calculated using power analysis; considering the margin of error ($\alpha= 0.05$), effect size ($f= 0.347$) and power 80% ($1-\beta= 0.80$) values and research design, the sample calculation was made for the Chi-Square test and a total of 66 people were determined. Considering the losses, the number of patients included in the sample was planned to be 86 patients (43 intervention group, 43 control group), 30% above the calculated value, and the study was completed with 71 patients. According to body mass index, weight status was stratified into four groups as underweight ($\leq 18.49 \text{ kg/m}^2$), normal weight (18.5 kg/m^2 - 24.9 kg/m^2), overweight (25kg/m^2 - 29.9kg/m^2) and obese ($\geq 30\text{kg/m}^2$).

Body Mass Index	Intervention Group	Control Group
Underweight	1	1
Normal Weight	8	12
Overweight	17	14
Obese	11	7
Total	37	34
General Total		71

Statistical Analysis

Statistical analysis of the research data was performed in the "Statistical Package for the Social Sciences (SPSS) 25.0" statistical package program (PASW Inc., Chicago. IL.USA) under the supervision of a statistical expert. In descriptive statistics; number and percentage distributions were shown and mean (mean) \pm standard deviation (SD) values were given. Demographic quantitative data were compared between the groups by Mann Whitney U test. The distribution of qualitative characteristics of the patients in the groups was analyzed using Pearson Chi-square test or Fisher's exact probability test. "Kaplan Meier - Survival Time" analyses were performed for the duration of pressure ulcer development. General Linear model analysis was performed for effect size. For repeated measures, changes in groups were

analyzed using the nonparametric Brunner Langer (F1 LD F1 model) method. Since only one patient in the intervention group developed pressure ulcers, intra-group statistical analysis could not be performed. The results were evaluated at 95% confidence interval and $p<0.05$ significance level.

Results

Socio-demographic characteristics, data on health status, pressure injury development risk assessment scale score, averages of some laboratory findings, and interface pressure values measured from pressure points of patients in the intervention and control groups in intensive care clinics are homogeneously distributed. Pressure injuries developed in 2.70% of the patients in the intervention group and 14.70% of the patients in the control group, the difference between them wasn't statistically significant ($p=0.098$). The effect size is 0.216 and has a low/medium effect size. Injury development time was 16 days in the intervention group and 6.00 ± 2.0 days in the control group (earliest 3rd day, latest 8th day), the difference between them was not statistically significant ($p=0.137$). Pressure injury developed in one underweight, one normal weight, and three obese patient in the control group and one obese patient in the intervention group, the difference between them was statistically significant ($p=0.006$).

In the control group, one patient with underweight, one patient with normal weight and three patients with overweight developed pressure injuries and the difference between them was statistically significant ($p=0.003$). Since only one of the obese patients in the intervention group developed pressure injuries, the development of pressure injuries according to body mass index could not be evaluated. The risk of pressure injury development is higher in underweight and obese patients, and less in overweight patients.

Pressure injuries developed in the gluteal area and sacrum in the patient in the intervention group, and in the sacrum in 8.8% of the patients in the control group, there was no statistically significant difference between them ($p=0.143$).

Conclusion

It was concluded that the frequency of position changes should be done with a personalized program for each patient, not at routine two-hour intervals, and the risk of pressure injury development is higher in low-weight and obese patients, while it is less in overweight patients.

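### Time to pressure injury appears to be compared in the six injured patients only; the uninjured should be censored, and the number randomised stated

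*Combined protocol and SAP*

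**What the plan says.** The document's title makes development time of pressure ulcers the outcome. The Statistical Analysis section names a Kaplan-Meier analysis for it but gives no censoring rule, length of follow-up or test for comparing the arms.

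Under Setting/Participants, the calculated sample is 66. Allowing for losses, the number was "planned to be 86 patients (43 intervention group, 43 control group), 30% above the calculated value". The same sentence adds that "the study was completed with 71 patients", and the table shows 37 intervention and 34 control patients. The document does not give the number randomised, the losses by arm with reason or day, the analysis population, or a rule for missing outcomes.

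The Results section reports: "Pressure injuries developed in 2.70% of the patients in the intervention group and 14.70% of the patients in the control group", with p=0.098. Time to injury is given as 16 days in the intervention arm and 6.00 ± 2.0 days in the control arm (earliest day 3, latest day 8), with p=0.137.

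**The concern.** In a time-to-event question, a patient who stays uninjured contributes injury-free days up to the last skin check. Comparing injury days among injured patients only discards that information. It asks when injury happened in those who had one, and patients selected by their outcome are no longer the randomised groups. The printed time summary sets one patient's day against a mean over five patients, so it cannot include anyone uninjured.

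The second issue is who counts in the rate comparison. An allowance for losses, followed by the word completed, suggests that some patients may have been allocated and then left. In intensive and palliative care, leaving may be related to how ill the patient is, and so to injury risk. With one injury against five, a handful of unknown outcomes could move the result across 0.05 in either direction.

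**Working it through.** **1. The rate comparison reproduces on 37 and 34.** 1/37 = 2.70% and 5/34 = 14.7%. The two-sided Fisher exact test gives p=0.0975 (printed 0.098). The effect size also matches: phi = |1×29 − 36×5| / √(37×34×6×65) = 151/700.4 = 0.216, as printed. There are 6 injured and 71 − 6 = 65 uninjured patients.

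**2. The time comparison reproduces on the six injured patients.** Assume injury times in whole days. Five control values with mean 6.0, minimum 3 and maximum 8 can be chosen in five ways, with SDs 2.74, 2.35, 2.12, 2.00 and 1.87. Only 3, 5, 7, 7, 8 has SD 2.0. Set against day 16:

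- U = 5, because day 16 exceeds all five control days; its null mean is 1×5/2 = 2.5.
- Variance with one tied pair = (1×5/12) × [7 − (2³ − 2)/(6×5)] = 0.4167 × 6.8 = 2.833.
- z = 2.5/√2.833 = 1.485, two-sided p=0.1375 (0.13749 unrounded; printed 0.137).

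This is the asymptotic test without continuity correction. A log-rank test on the same six patients gives 0.126, which does not match.

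**3. Log-rank on all 71, uninjured patients censored.** Inputs are the inferred control days and the intervention injury on day 16. The follow-up days of the uninjured are not in the document, so two illustrative cases are used.

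| Day | At risk (control/all) | Injuries | Expected in control | Variance |
|---|---|---|---|---|
| 3 | 34/71 | 1 | 0.4789 | 0.2496 |
| 5 | 33/70 | 1 | 0.4714 | 0.2492 |
| 7 | 32/69 | 2 | 0.9275 | 0.4901 |
| 8 | 30/67 | 1 | 0.4478 | 0.2473 |
| 16 (if followed) | 29/66 | 1 | 0.4394 | 0.2463 |

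- All uninjured censored at day 10: the day-16 injury adds nothing, as only that patient is still at risk. Expected 2.3256, variance 1.2361; (5 − 2.3256)²/1.2361 = 5.79, p=0.016.
- All uninjured followed past day 16: expected 2.7650, variance 1.4824; (5 − 2.7650)²/1.4824 = 3.37, p=0.066.

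**4. Rate comparison if more than 71 were randomised.** Assumption not in the document: 43 + 43 were randomised, so 43 − 37 = 6 intervention and 43 − 34 = 9 control outcomes are missing.

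| Injuries among the missing | Intervention | Control | Fisher p |
|---|---|---|---|
| None | 1/43 | 5/43 | 0.20 |
| At observed rates (6×1/37 = 0.16; 9×5/34 = 1.32; rounded to 0 and 1) | 1/43 | 6/43 | 0.11 |
| 3 of 9 control, 0 of 6 intervention | 1/43 | 8/43 | 0.030 |
| 3 of 6 intervention, 0 of 9 control | 4/43 | 5/43 | 1.0 |
| All 9 control, 0 intervention | 1/43 | 14/43 | 0.0003 |
| All 6 intervention, 0 control | 7/43 | 5/43 | 0.76, direction reversed |

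Fewer missing patients could also matter: two more controls, both injured, would give 1/37 against 7/36, p=0.028. If exactly 71 were randomised, none of these cases arises.

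**The case against.** A reader might infer that 15 patients were randomised, lost and then dropped, and that p=0.098 and p=0.137 therefore rest on an outcome-related selection of completers. The document does not support this. The figure 86 is a plan; recruitment may simply have ended at 71, above the required 66, and 37 and 34 may be everyone allocated. Nor does p=0.137 look like a 71-patient result, since it matches a test on six. The extremes in step 4 are bounds, not expectations: the smallest p needs all nine missing controls injured against 14.7% observed, and at the observed rates p is 0.11, close to the printed value.

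It can also be said that restoring uninjured leavers hardly moves the log-rank result. That is right. On 43 + 43 with nobody further injured, p is 0.088 or 0.022 instead of 0.066 or 0.016. If the 15 are censored at day 3, it is 0.069 or 0.017. The larger change comes from bringing in the 65 uninjured patients already held, and it depends on follow-up days that are not reported.

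Two further points stand. The match to a Mann-Whitney test is an inference: a Kaplan-Meier analysis may have been run and not reported, and some unreported follow-up pattern might give a similar p-value by another route. Also, censoring at leaving assumes that leaving is unrelated to injury risk, so a log-rank test alone does not remove the bias that worries us.

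**Conclusion.** The concern holds in two parts of different strength.

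The firmer part is the time comparison. Its summary covers injured patients only, and its p-value matches a six-patient Mann-Whitney test, so 65 uninjured patients appear to be left out although Kaplan-Meier is named. Censoring them would replace p=0.137 with 0.066 or 0.016 in the two illustrative cases, so the significance statement could change. This rests on whole-day injury times and on assumed follow-up, but not on how many were randomised.

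The conditional part is the rate comparison. The number randomised is a reporting gap, and loss after allocation is plausible but not shown. If more than 71 were randomised, six events make the comparison fragile. Stated power is not the issue: 71 patients give 0.832 at the planned effect size of 0.347.

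**What to change.** - Make the main analysis a Kaplan-Meier and log-rank comparison of all randomised patients in their allocated arm. Time runs from allocation to first pressure injury; uninjured patients are censored at their last skin assessment.
- Withdraw the injured-only comparison as a test of the arms. The injury days can stay as description.
- Add a sensitivity analysis with death as a competing event.
- State the numbers randomised, lost (by arm, reason and day) and analysed, and the follow-up days of the uninjured patients.
- If more than 71 were randomised, add a missing-outcome sensitivity analysis that shows the observed-rate case as well as the bounds, and keep the 71-patient result as secondary. If exactly 71 were randomised, one sentence saying so settles that part.

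The cost is a short re-analysis and a few lines of text, with no new patients, provided that skin-check dates are held, including for anyone who left early. The p-values may move in either direction.

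### Kaplan-Meier is the only method named for time to pressure ulcer in intensive and palliative care, with no stated handling of death or discharge, and the reported time comparison appears to use only the six ulcer patients

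*Combined protocol and SAP*

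**What the plan says.** The title makes ulcer development time the outcome. The Setting/Participants section says the trial was "conducted in the intensive care and palliative care units of a university hospital". The Statistical Analysis section says that Kaplan-Meier survival-time "analyses were performed for the duration of pressure ulcer development"; no other time-to-event method is named. For categorical characteristics, the distribution between groups "was analyzed using Pearson Chi-square test or Fisher's exact probability test". The sample size rests on a comparison of proportions, not of times: "the sample calculation was made for the Chi-Square test and a total of 66 people were determined".

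The planned total was 86 (43 per arm), which allows for losses, and the study was completed with 71 (37 intervention, 34 control). Neither the methods nor the results mention death, discharge, a censoring rule, a follow-up horizon or competing risks. The Results section gives ulcer proportions of 2.70% and 14.70% (p = 0.098, effect size 0.216). It gives ulcer times of 16 days in intervention and 6.00 ± 2.0 days in control, range 3 to 8 (p = 0.137). It reports no Kaplan-Meier curve, median or probability.

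**The concern.** A patient who dies without an ulcer can no longer develop one. Two-state Kaplan-Meier has no place for that event, so the patient must be either censored or left out.

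- **Censored.** The estimate treats the patient as still able to develop an ulcer later. Then 1 minus Kaplan-Meier describes ulcer risk in a world without death, and it is at or above the risk these patients face.
- **Left out.** The comparison is restricted by something that happened after randomisation, and the arms may no longer be comparable.

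Discharge raises a related question, because observation stops for a reason linked to the patient's condition. The text does not say which route was taken. The 15 patients between 86 planned and 71 completed are not explained. If 43 per arm were enrolled (an assumption), 6 in intervention and 9 in control are unaccounted for.

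The Conclusion section recommends individual scheduling over routine two-hour turning. A reader weighing that needs to know how patients who died or left early entered the time analysis.

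**Working it through.** **1. What the reported ulcer risks are.** Inputs from the Results section and the group table: 1 of 37 and 5 of 34.

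- 1/37 = 2.70% and 5/34 = 14.7%, as reported.
- Fisher's exact test on 1/36 against 5/29 gives p = 0.0975 (reported 0.098). Pearson chi-square is 3.30, p = 0.069.
- Phi = √(3.30/71) = 0.216, as reported.

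The published risks are therefore crude proportions tested by Fisher, not 1 minus Kaplan-Meier.

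**2. What the reported time comparison is.** The control arm has five ulcer times with mean 6, minimum 3, maximum 8 and SD 2.0. If times are whole days, the deviations from 6 sum to 0 and their squares sum to 4 × 2.0² = 16. Two deviations are −3 and +2, so the other three sum to +1 with squares summing to 16 − 13 = 3. Only −1, +1, +1 fits, so the days are 3, 5, 7, 7, 8. These days are inferred; the document does not list them.

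Mann-Whitney of the single value 16 against these five, with one tied pair:

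- The difference of U from its mean is 5 − 2.5 = 2.5.
- Variance = (1 × 5/12) × [7 − 6/(6 × 5)] = (5/12) × 6.8 = 2.833.
- z = 2.5/√2.833 = 1.485, two-sided p = 0.1375 (reported 0.137).

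A log-rank test on the same six patients gives p = 0.126. A log-rank test on all 71, assuming no censoring before day 16, gives p = 0.066. Only the rank test on the six ulcer patients matches. It could say little in any case: the observed ordering is already the most extreme possible for one against five, and its exact two-sided p is 2/6 = 0.333.

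**3. Size of the Kaplan-Meier problem if deaths are censored.** The documents give no number of deaths, so an assumed range is used. Let p be the cumulative incidence of ulcer and d that of death without ulcer, with constant cause-specific hazards. Then

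- total cumulative hazard L = −ln(1 − p − d)
- cumulative ulcer hazard H = L × p/(p + d)
- 1 − KM = 1 − exp(−H)

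Worked case, control, d = 0.20: L = −ln(1 − 0.1471 − 0.20) = 0.426; H = 0.426 × 0.1471/0.3471 = 0.181; 1 − KM = 16.5%.

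| Assumed ulcer-free deaths | Control 1 − KM (p = 14.7%) | Intervention 1 − KM (p = 2.7%) | Arm gap (crude 12.0 points) |
|---|---|---|---|
| 20% | 16.5% | 3.0% | 13.5 |
| 40% | 19.2% | 3.5% | 15.7 |
| 60% | 23.7% | 4.2% | 19.5 |

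Timing matters too. If all assumed deaths came before the first control ulcer, 1 − KM in control would be 5/(34 − 6) = 17.9% with 6 deaths and 5/(34 − 12) = 22.7% with 12.

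**4. What unequal mortality does to each estimate.** Give both arms H = 0.181, with 20% ulcer-free deaths in one and 55% in the other (assumed). 1 − KM is 16.5% in both. The cumulative incidence is 14.7% in the first and 11.0% in the second. Under independent hazards, a mortality difference moves the cumulative incidence and not Kaplan-Meier.

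**The case against.** The strongest reply is that no published number is shown to be wrong. A reader might infer that deaths were censored and that the reported ulcer risks are inflated. The document supports neither inference. It never says what was done with deaths, and step 1 shows that 2.70% and 14.70% are crude proportions. If every patient was followed to ulcer, death or a common horizon, those proportions already equal the cumulative incidence. If some patients left observation early, they would tend to understate risk. The death rates in step 3 have no source in the document. On the ratio scale the arms barely move: 14.7/2.7 is about 5.4 crude, and 23.7/4.2 is about 5.7 at 60% deaths.

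A reader might also infer that unequal mortality would turn a Kaplan-Meier difference into a disguised mortality effect. Step 4 shows that this fails when the hazards are independent. The log-rank test with deaths censored remains a valid cause-specific comparison, so Gray's test has no claim to replace it.

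Finally, the trial was sized on proportions, so the time analysis may have been secondary in practice. All of this stands, and it limits the claim about size. It does not supply the missing rule for death and discharge. Nor does it explain why the comparison of the title outcome matches a test on the six ulcer patients.

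**Conclusion.** The point holds in a conditional form. Kaplan-Meier is the only time-to-event method named for the title outcome, in units where death and discharge before an ulcer are foreseeable, and the handling of neither is stated. If deaths are censored, 1 minus Kaplan-Meier would exceed the risk patients face. The excess is about 2 to 9 percentage points in control and 0.3 to 1.5 in intervention, under constant hazards and assumed ulcer-free deaths of 20% to 60%. If deaths are dropped, the problem is selection after randomisation, and its direction and size cannot be worked out from the document.

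The reported crude risks are not shown to be biased in this way. The reported p = 0.137 appears to come from the six ulcer patients only, which conditions on the outcome and leaves the stated Kaplan-Meier analysis unreported. That inference rests on whole-day times and on the match to a tie-corrected Mann-Whitney test; the document does not name the test used. This should be corrected, but it does not by itself overturn a reported result.

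**What to change.** - State the follow-up horizon, the censoring rule, and how death and discharge before an ulcer are handled.
- For all randomised patients, report the Aalen-Johansen cumulative incidence of first pressure injury by arm, with death before injury as a competing event and with confidence intervals.
- Keep the log-rank test as the cause-specific comparison and give Gray's test as a supplement. Say which question each answers.
- Tabulate deaths and discharges by arm, and account for the difference between 86 planned and 71 completed.
- Label the 16 against 6.00 ± 2.0 days as a description of patients who developed an ulcer, and do not use it as the between-arm test of development time. If any Kaplan-Meier curve is shown, do not present 1 minus Kaplan-Meier as ulcer incidence.

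The cost is retrieving dates of death and discharge from hospital records, a short reanalysis and one more reported test. With six events the intervals will stay wide whichever estimator is used, and the report should say so.

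### The Results place the same three control-arm injuries in both obese and overweight patients, and give the arm comparison without an odds ratio, risk difference or confidence limits

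*Combined protocol and SAP*

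**What the plan says.** **Arm comparison.** The Results state: "Pressure injuries developed in 2.70% of the patients in the intervention group and 14.70% of the patients in the control group". They then give p=0.098 as not significant, followed by "The effect size is 0.216 and has a low/medium effect size". The index behind 0.216 is not named. The Statistical Analysis section says "General Linear model analysis was performed for effect size", without listing model terms, and "The results were evaluated at 95% confidence interval", together with a 0.05 significance level. No confidence limits appear for this comparison.

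**Injuries by BMI.** The first Results paragraph puts one control injury in an underweight patient, one in a normal-weight patient and the rest in "three obese patient in the control group". It adds one obese patient in the intervention arm and reports p=0.006. The next paragraph gives the same control-arm breakdown except that "three patients with overweight developed pressure injuries", with p=0.003. The Conclusion then states that "the risk of pressure injury development is higher in low-weight and obese patients, while it is less in overweight patients".

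**The concern.** The control arm had five injuries in all, so the two breakdowns cannot both be true. The difference is not cosmetic. On one reading no overweight patient was injured; on the other, overweight patients had half of the six injuries in the trial. The statement about overweight patients in the Conclusion has numerical backing on the first reading only.

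The wording around p=0.006 adds a second difficulty. The sentence lists control and intervention injuries together and calls the difference between them significant, so it can be read as an arm effect within BMI groups.

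The arm comparison has a smaller, separate problem. A unitless index labelled low to medium does not show how much or how little the six events establish. A reader has to work out what 0.216 is and then compute the contrast and its limits.

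**Working it through.** **Inputs.** Arm totals 37 and 34, and BMI group sizes (intervention + control), from the table under Setting/Participants: underweight 1+1=2, normal weight 8+12=20, overweight 17+14=31, obese 11+7=18. Events: one in the intervention arm ("Since only one patient in the intervention group developed pressure ulcers"), and 14.70% of 34 = 5 in the control arm. Check: 1/37 = 2.70%, 5/34 = 14.71%.

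**1. Reproduce the arm comparison.**
- Pearson chi-square = 71 × (1×29 − 36×5)² / (37×34×6×65) = 3.300.
- Phi = √(3.300/71) = 0.2156, the reported 0.216.
- Fisher, two-sided. With six events fixed, the probability of 0, 1 or 6 of them in the intervention arm is 0.0094, 0.0719 and 0.0162. These are the outcomes no more likely than the one observed, and they sum to 0.0975, the reported 0.098.
- Uncorrected Pearson (0.069) and Yates (0.165) do not match.

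**2. Add limits to the arm comparison.**
- Risk difference = 0.0270 − 0.1471 = −0.1200.
- Wilson limits: 0.0048 to 0.1382 (intervention) and 0.0645 to 0.3013 (control).
- Newcombe lower = −0.1200 − √[(0.0270−0.0048)² + (0.3013−0.1471)²] = −0.276.
- Newcombe upper = −0.1200 + √[(0.1382−0.0270)² + (0.1471−0.0645)²] = +0.018.
- Sample odds ratio = (1×29)/(36×5) = 0.161. Conditional estimate 0.165, exact 95% limits 0.003 to 1.59.

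**3. Test both BMI readings** (Fisher-Freeman-Halton exact test; injuries/patients).

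| Reading | Table | Underweight | Normal | Overweight | Obese | Exact p | Reported |
|---|---|---|---|---|---|---|---|
| Obese | Control | 1/1 | 1/12 | 0/14 | 3/7 | 0.0032 | 0.003 |
| Obese | Both arms | 1/2 | 1/20 | 0/31 | 4/18 | 0.0065 | 0.006 |
| Overweight | Control | 1/1 | 1/12 | 3/14 | 0/7 | 0.120 | 0.003 |
| Overweight | Both arms | 1/2 | 1/20 | 3/31 | 1/18 | 0.272 | 0.006 |

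The pooled obese value is 0.00646 before rounding. Pearson versions match neither reported figure: 0.0046 and 0.0072 with obese, 0.048 and 0.170 with overweight (control arm, then both arms).

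**4. What p=0.006 tests.** It reproduces as BMI group against injury with the arms pooled. Comparing arms within obese patients, on the obese reading, gives 1/11 against 3/7, Fisher p=0.245.

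**5. What each reading says about overweight patients** (post hoc Fisher tests, arms pooled).
- Obese reading: overweight against obese, 0/31 vs 4/18 (22.2%), p=0.014. Overweight against normal weight, 0/31 vs 1/20 (5.0%), p=0.39. The upper 95% limit for 0/31 is 1 − 0.025^(1/31) = 11.2%.
- Overweight reading: 3/31 (9.7%) against 1/18 (5.6%) and against 1/20 (5.0%), p=1.00 for each.

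**The case against.** The strongest reply on BMI is that the contradiction is one wrong word. Both reported p-values fit obese, as do the first breakdown and the Conclusion. That is persuasive about which counts were analysed. It does not verify which patients were injured, so a source check is still needed, but the likely answer should be stated.

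On the arm comparison, the reply is that the mention of a 95% confidence interval sits beside the significance level and may only describe the error rate. Both percentages and denominators are given, so the limits can be derived. This also largely stands: the gap is one of reporting, and no analysis is wrong.

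A reader might infer three stronger points that the documents do not support:
- *The overweight counts would reverse the BMI conclusion.* They would not. With p=1.00 against both neighbouring groups, they would leave it unsupported without showing the opposite.
- *The overweight claim fails even on the obese reading, because 0/31 vs 1/20 gives p=0.39.* That is only one comparison. The document contrasts overweight with underweight and obese patients, and 0/31 vs 4/18 gives p=0.014.
- *The arm comparison needed BMI adjustment.* Nothing shows this. The crude Fisher test is valid, BMI group is reasonably balanced between arms (chi-square 1.86, 3 df, p=0.60), and the unnamed model terms are not evidence of a defect.

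**Conclusion.** The contradiction is real, and one of the two sentences is wrong. The evidence points to the second, where overweight is probably a slip for obese. If so, the two BMI p-values stand, and the lower risk in overweight patients is shown only relative to obese patients, by a post hoc contrast on six events in the whole trial. It is not shown relative to normal weight. If the slip is the other way, both p-values are wrong and the statement about overweight patients has no support.

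The arm result of p=0.098 with phi 0.216 is correct but under-reported. The data are compatible with anything from about a 28-point reduction in incidence to about a 2-point increase. The conclusion of no significant difference does not change.

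This rests on event counts of 1 and 5 derived from the percentages and arm totals, on the BMI group sizes as tabulated, and on two-sided tests. The document does not state sidedness or name the incidence test; two-sided Fisher is taken because it reproduces 0.098.

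**What to change.** 1. Check the three control-arm injuries against source data and correct whichever sentence is wrong.
2. If they were in obese patients, state in the Results and Conclusion that the lower overweight risk is relative to obese patients (0/31 vs 4/18, post hoc p=0.014), is not shown against normal weight (0/31 vs 1/20, p=0.39), and rests on six events.
3. If they were in overweight patients, replace p=0.006 and p=0.003 (exact values 0.272 and 0.120) and withdraw the statement that overweight patients are at less risk.
4. If p=0.006 is retained, describe it as an association of BMI group with injury pooled across arms, not as a difference between arms.
5. Keep Fisher's test as the arm comparison and name it. Label 0.216 as phi. Report beside it the odds ratio 0.165 (exact 95% CI 0.003 to 1.59) and the risk difference of -12.0 points (Newcombe 95% CI -27.6 to +1.8).

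The cost is one look at source records and a few lines of text from tables already in hand. No new data or further modelling are needed. The one drawback is that the wide intervals will make plain how little six events can show.

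### Time to pressure ulcer, the title outcome, is reported only for the six injured patients, with p=0.137 from an unnamed test and no estimate that counts the 65 event-free patients

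*Combined protocol and SAP*

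**What the plan says.** The title puts the outcome as the effect of BMI-based repositioning frequency "ON PRESSURE ULCER DEVELOPMENT TIME". The Statistical Analysis section says of Kaplan-Meier survival time that "analyses were performed for the duration of pressure ulcer development". It names no between-arm test for that outcome, and it assigns the Mann-Whitney U test to demographic quantitative data only. Setting/Participants reports that "the study was completed with 71 patients", 37 intervention and 34 control, against 86 planned.

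The Results section first gives incidence: "Pressure injuries developed in 2.70% of the patients in the intervention group and 14.70% of the patients in the control group" (p=0.098). On time it says "Injury development time was 16 days in the intervention group" and 6.00 ± 2.0 days in control, with "earliest 3rd day, latest 8th day), the difference between them was not statistically significant" (p=0.137). It gives no survival estimate, ulcer-free proportion over time, number at risk, length of follow-up or account of censoring, and no test name.

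**The concern.** A mean, SD and range of injury days can describe only patients who were injured. Whether a patient is injured is itself an outcome after randomisation, so comparing days among the injured does not compare the randomised groups. It also leaves out the patients in whom repositioning may have worked best, those who were never injured. Kaplan-Meier analysis exists to bring them in.

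At stake is how the title outcome is read. If p=0.137 comes from one intervention value against five control values, its non-significance reflects the size of that comparison and tells the reader nothing about whether injury was delayed. The analysis that could address delay is said to have been done and is not shown.

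**Working it through.** **1. Who the times cover.** Group sizes 37 and 34 and the two percentages are in the document. 1/37 = 2.70% and 5/34 = 14.71%, so there were 1 and 5 injuries. Event-free: 37 − 1 = 36 intervention and 34 − 5 = 29 control, together 65 of 71 (92%).

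**2. The control injury days.** Assume whole days. Five values with mean 6.00 sum to 30. SD 2.0 means a sum of squared deviations of 4 × 2.0² = 16. The minimum of 3 and maximum of 8 contribute 9 + 4 = 13, leaving three values whose deviations from 6 sum to 1 and whose squares sum to 3: −1, +1, +1. The only set is {3, 5, 7, 7, 8}.

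**3. Reproducing p=0.137.** Mann-Whitney test of {16} against that set, two-sided, asymptotic, tie-adjusted, no continuity correction:
- U = 5; expected U = 1 × 5/2 = 2.5.
- Variance = (1 × 5/12) × [7 − (2³ − 2)/(6 × 5)] = (5/12) × 6.8 = 2.833.
- z = 2.5/√2.833 = 1.485; p = 0.1375 (0.13749 unrounded, which prints as 0.137).

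Other tests on the same six patients do not match: Mann-Whitney with continuity correction 0.235, exact Mann-Whitney 0.333, t-test 0.010, log-rank 0.126, Breslow 0.181, Tarone-Ware 0.148.

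**4. What a 1-against-5 rank test can show.** The single value can take any of six ranks, so the smallest exact two-sided p is 2/6 = 0.333. There are 56 whole-day control sets that run from day 3 to day 8. Over all of them the asymptotic p goes from 0.083 ({3, 3, 3, 3, 8}) to 0.143 (no ties). None is below 0.05.

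**5. What an all-patient log-rank test might give.** This cannot be computed, because follow-up of the 65 event-free patients is not stated. Two illustrations:
- *All event-free patients followed to day 16 or later.* Expected intervention events are 37/71 + 37/70 + 2 × 37/69 + 37/67 + 37/66 = 0.521 + 0.529 + 1.072 + 0.552 + 0.561 = 3.235. Observed = 1; variance = 1.482. Chi-square = (1 − 3.235)²/1.482 = 3.37; p = 0.066.
- *Staggered follow-up, same distribution in both arms.* With 3 days plus an exponential time of mean 5 days, 95% of simulated p-values lie between about 0.01 and 0.18, and about 8% exceed 0.1365. With a mean of 30 days the range narrows to about 0.04 to 0.10.

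**The case against.** Several points on the other side deserve weight.

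*The origin of p=0.137 is inferred.* This stands. Under short, equal follow-up an all-patient log-rank p as large as 0.137 is not rare. Stopping observation of all 71 patients at day 5 gives 0.1372, although that would discard four of the six reported injuries. The rank-test match makes an injured-only test probable, not proven.

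*The paper claims no delay.* It calls the time difference non-significant, its conclusion does not mention delay, and incidence is already compared in all 71 patients (p=0.098). True, but incidence is not the title outcome, and a non-significant time result is still printed as a finding.

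*Six events give an imprecise answer.* Also true. That is a reason to show the interval, not to leave out the estimate.

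Three stronger readings are tempting, and the documents do not support them:
- A reader might infer that a correct analysis would have been significant. Log-rank p-values of 0.016 to 0.040 do arise, but only if all 65 event-free patients are censored on one common day between day 5 and day 15 while injured patients stay under observation. Nothing in the document suggests this.
- A reader might point to day 8, when all five control injuries and no intervention injury had occurred. That day is picked from the injury times, and the figures behind it are already printed.
- A reader might see a contradiction with "Since only one patient in the intervention group developed pressure ulcers, intra-group statistical analysis could not be performed". That sentence concerns analysis within a group, and the Results section ties the same limit to analysis by BMI. It does not bear on a between-arm comparison.

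**Conclusion.** The omission is certain and needs no reconstruction: an analysis stated as done for the title outcome is not reported, and the only times given come from 6 of 71 patients. That p=0.137 is an injured-only Mann-Whitney test is probable; it rests on whole-day times and a two-sided asymptotic test. If it is, it is not a comparison of the randomised groups, and with 1 against 5 it could not have reached p<0.05. Its non-significance is then uninformative about delay. The size and direction of any change on re-analysis are unknown. The illustrative log-rank values (0.066; about 0.01 to 0.18) depend on assumed follow-up and imply no significant benefit. This should be corrected before the time result is relied on.

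**What to change.** 1. State the test and the patients behind p=0.137. If it is injured-only, withdraw it as a between-arm test.
2. Keep the injury days as description, labelled as among injured patients.
3. For all 71 analysed patients, noting that 86 were planned, report the Kaplan-Meier curves with numbers at risk and follow-up by arm. Give ulcer-free proportions by arm, and their difference, with 95% CIs. Choose the reporting day from the follow-up distribution without reference to the injury times, while a reasonable number in each arm is still at risk. The last day on which both arms were observed would be a poor choice, since very few patients may remain.
4. Name the all-patient between-arm test (log-rank). With six events, a permutation p-value is an optional check; it assumes similar censoring in both arms.
5. State how death and discharge were handled, since the setting is intensive and palliative care. If they were common, report cumulative incidence as well.
6. Rest the reading on the estimate and its interval, and say that it is imprecise.

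The cost is a small re-analysis and a few sentences of text, with no new patients. If last-observation days were not recorded, the report should say that the survival comparison cannot be made.
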